8.5.2 Adverse Event Reporting

Adverse events which are not SAEs or Grade 2 or higher unexpected AEs, will be recorded on the appropriate case report form and sent to the SACCC for incorporation into annual reporting to the NIAID and DSMB.

8.5.3 Reporting to the IRB

The Principal Investigator (or delegate) must report adverse events and serious adverse events to the central IRB promptly in accordance with local regulations or policies, in addition to providing the information to the SACCC.

8.5.4 Reporting Pregnancy

A pregnancy will not be reported as an adverse event for follow-up purposes. All pregnancies that are identified during the study will be followed to conclusion and the outcome of each will be reported. If the pregnancy results in anything other than a normal birth or elective abortion of a healthy fetus, it will be reported as a serious adverse event.

8.6 Type and Duration of the Follow-up of Participants after Adverse Events

The site investigator must apply his or her clinical judgment as to whether an AE is of sufficient severity to require that the participant immediately be removed from the study. The investigator must institute any necessary medical therapy to protect a participant from any immediate dangers.

An AE will be followed until any of the following takes place: a) it is resolved, b) participant is stable, or c) a minimum of 30 days after participant is discontinued from the study, whichever comes first.

8.7 Participant Discontinuation

Participants may choose to withdraw from the study at any time, during a study visit, or afterwards in person, by telephone, or in writing.

Participants may be prematurely terminated from the study for the following reasons:

1. The participant elects to withdraw consent from all future study activities.
2. The participant is “lost to follow-up” (i.e., no further follow-up is possible because attempts to re-establish contact with the participant have failed).
3. The investigator no longer believes participation is in the best interest of the participant.

Participants will be notified, if possible, if they are discontinued from the study. No additional follow-up will be required.

8.8 Replacement of a Participant Who Discontinues Study Participation

URECA study participants will not be replaced after discontinuation. However, “lost” study participants who are subsequently relocated and who provide informed consent, may be re-activated.

9 Clinical Monitoring Structure

9.1 Site Monitoring Plan

Clinical site monitoring will be conducted according to the URECA Clinical Monitoring Plan (CMP) for ICAC-07 to ensure that human subject protection, study procedures, and laboratory and data collection processes are of high quality and meet sponsor, International Conference on Harmonisation, Good Clinical Practice, and regulatory guidelines. Representatives from the National Institute of Allergy and Infectious Diseases (NIAID) and/or the SACCC will visit each clinical site or meet with each clinical site via telephone during a specified timeframe according to the URECA CMP for ICAC-07. Key study personnel must be available to assist the visitors during these visits or attend the call if completed via telephone. Additional details regarding clinical site monitoring, including remote monitoring, are outlined in the URECA CMP and MOP for ICAC-07.

9.2 Safety Monitoring

Safety monitoring will be performed following the URECA Safety Management Plan (SMP).

9.2.1 Medical Monitor Review

The DAIT Medical Monitor will review all serious adverse events and Grade 2 or higher unexpected adverse events immediately upon notification by the SACCC. The Medical Monitor will review reports prepared by the SACCC of all adverse events at least quarterly.

9.2.2 DSMB Review

The DSMB will review any events as requested by the Investigators, SACCC, or DAIT Medical Monitor. They will review a listing of all adverse events once per year. Further, the DSMB will be informed of expedited SAEs at the same time as the central IRB.

10 Statistical Considerations

10.1 Overview

The URECA continuation into age 17 years has the following specific aims that will be accomplished under this protocol. Mechanistic and substudy aims will be addressed in separate analytic plans.

1. To determine the wheezing, asthma and atopy phenotypes in minority children growing up in poor urban neighborhoods as they develop from birth through adolescence.
2. To longitudinally analyze the development of lung function and its relationship to asthma.
3. To identify which urban exposures (allergens, pollutants, microbes, viral infections, stress) from early life onward affect the development and natural history through adolescence of asthma, allergic rhinitis and allergic sensitization.
4. To determine the association of pre-pubertal obesity and the effect of pubertal changes in adiposity and sex hormones on lung growth and asthma onset, prevalence and morbidity.

10.2 Endpoints

10.2.1 Primary Endpoints

The primary endpoints for this phase of the URECA study are wheezing, asthma and atopy phenotypes in minority children.

10.2.2 Secondary Endpoints

Secondary endpoints include:

1. Methacholine responsiveness – this will be ascertained at age 14/15.
2. Pulmonary function – pre- and post- bronchodilator spirometry and impulse oscillometry will be measured once at age 14/15, and once at age 16/17.
3. Allergic sensitization – defined as a dichotomous variable (aeroallergen-specific IgE by skin test or serum test) or as a continuum (number of positive skin or sIgE tests, sum of sIgE values).
4. Allergic rhinitis – chronic seasonal or perennial rhinitis and corresponding allergen-specific IgE or skin test.

10.3 Measures to Minimize Bias

The primary threat to validity in a cohort study such as URECA is missing data due to loss-to-follow-up or missed visits and procedures. The URECA study to date has done a remarkable job of retaining the participants, with 73% of the original cohort still active at age 14/15. In recent phases of URECA, >85% of expected visits have been completed.

Missing data create problems because fewer observations will reduce the power of the study. If the data are nonrandomly missing, i.e. associated with either the predictor or the outcome, estimates generated in the analyses may be biased, possibly leading to invalid inferences. For example, children with asthma symptoms might miss their spirometry measurement. This can lead to nonrandomly missing data and can complicate analyses.

The pattern of missing data will be explored for every analysis. Missing data can generally be characterized as being in 1 of 3 classes--missing completely at random, missing at random, and not missing at random (also called nonignorably missing or informatively missing).¹¹⁻¹³ If data are missing completely at random or missing at random, we will select the most appropriate available statistical method, typically a linear or generalized linear model or survival model that addresses the specific question. If the data are informatively missing, selection of the appropriate technique will require further consideration. Currently the statistical community has not reached a consensus on how to best address the issue of informatively missing data, but many approaches have been proposed.¹²⁻¹⁸ Analyses conducted by Rho statisticians for multiple projects suggest in many cases the best approach is to use a linear mixed model even in the face of informatively missing data.¹⁹ URECA analyses to date have shown most missing data to be the result of missed visits or sample analysis problems, and not informatively missing.

10.4 Analysis Plan

10.4.1 Primary Analysis of Primary Objective

The purpose of the primary analysis in the fourth phase of URECA will be to identify wheezing and asthma phenotypes in the children through the age of 17 years. Furthermore, we will identify risk factors for the asthma phenotypes related to environmental exposures, immune responses and biomarkers, weight and fitness status, and airway and environmental microbiota.

Using the extensively and longitudinally characterized URECA cohort, we will:

1. Categorize URECA subjects into already described early life patterns of wheezing (Tucson Children's Respiratory Study, Avon Longitudinal Study of Parents and Children, Prevention and Incidence of Asthma and Mite Allergy) and development of atopic disorders (Manchester) to determine if these patterns are indeed observed among inner-city American children.
2. Using longitudinal data obtained from the URECA cohort through the age of 17 years, we will perform a cluster analysis to identify patterns of wheezing, allergic sensitization and lung function over time. In URECA the comprehensive longitudinal measurements within a child allow the application of techniques such as latent class analysis where periods have the greatest impact on the development and maintenance of asthma through the teen years. In particular, symptoms, exacerbations, allergy, immunologic measures, BMI, fitness, psychosocial factors and objective measurements of lung function, spirometry, eNO and IOS will define clusters of asthma phenotypes based on a combination of these variables. We will consider latent class analysis and other clustering techniques to identify phenotypes in URECA V.

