1.1 Background Information

The Urban Environment and Childhood Asthma (URECA) birth cohort study was initiated in 2004 by the Inner City Asthma Consortium (ICAC) to conduct comprehensive studies to define early life exposures that promote the development of disturbances in immune function that will lead to allergic sensitization and asthma.^{1,2} The study recruited a cohort of children from urban areas in economically disadvantaged neighborhoods in New York City, Boston, Baltimore, and St. Louis. The clinical teams collaborated with community leaders and obstetrical groups to recruit a study group representing mothers and children (70% Black, 20% Latino or Hispanic) residing in urban areas of poverty and difficult living circumstances that are reflective of US inner cities.² The overall goal of these studies has been to gain greater insight into the unique effects of the inner-city environment on the development of asthma, and from these findings identify more effective treatments in this high-risk group of children and to begin efforts to prevent the expression of asthma in inner-city youth. The study design focused on collecting data on key environmental exposures (stress, viral infections, allergens, microbes, indoor pollutants), measures of immune development (PBMC cytokine responses, T regulatory cells, allergen-specific IgE and IgG, plasma cytokines), and indicators of clinical outcomes (wheezing episodes, allergic sensitization, medication use, lung function testing). To accomplish these goals, study participants had yearly clinic visits with quarterly phone calls in between.

[figure not shown]
Retention has been highly successful. Despite a historic lack of connection to the medical establishment and atmosphere of distrust of participation in clinical research, the clinical teams used frequent contacts, neighborhood resources, home visits, and an attitude of inclusiveness to maintain retention rates that has far exceeded expectations.³ It is notable that **73% of the children (now ages 13-15 years) remain active participants** (Figure 1, data from November 2020).

The URECA III protocol was completed in March 2017, with the last of the 10-year clinic visits. The follow-on URECA IV protocol ends with the conclusion of ICAC funding on July 31, 2021 when the participants will be between 14 and 16 years old. The current URECA V protocol will be enacted April 1, 2021 and will allow for follow-up of the URECA participants into their 17th year.

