Aim 2 will test the hypothesis that early life exposure to allergens in the home in the absence of a diverse microbiome is associated with sensitization to those allergens and respiratory symptoms (perennial rhinitis and allergic asthma phenotypes). We will identify additional early life exposures that are associated with no sensitization, sensitization without clinical symptoms and sensitization with respiratory symptoms.

Aim 3 will integrate the diverse data available in URECA children to identify asthma endotypes and their predictors by: **a**) using advanced clustering techniques to identify respiratory and asthma phenotypes from longitudinal data, including upper and lower airway symptoms, allergic sensitization, lung function, BMI and psychosocial factors such as depression and risky behaviors; **b**) linking phenotypes to potential causative factors, such as specific environmental exposures (home microbiome and allergen exposure), AEC DNAm and gene expression patterns, upper airway microbial colonization, and serum hormone levels (e.g. insulin, sex hormones, adipokines); and **c**) identifying biomarkers to enable early identification of asthma endotypes.

[figure not shown]

Figure 2. Specific aims (numbered).

The results of these studies will link the pivotal early life exposures to airway epithelial cell DNAm and gene expression patterns, and ultimately to clinical expression of allergic diseases and asthma. These integrated data can be used to detect at-risk children at an early age, and from these pathways, develop and test interventions in early life to prevent allergy and asthma in urban children, and thus relieve a lifetime burden of asthma in this high-risk urban children.

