5.1.9 Fitness Testing

The Six-Minute Walk Test will be used at the 14/15-year time point to assess the participant's level of fitness.¹⁰ For this test the participant is asked to walk around two cones placed in a hallway 60 meters apart at a fast pace for six minutes. The number of meters walked is measured, as well as the participant's pulse and respiratory rate. The participant is asked to rate his or her level of fatigue on a visual analogue scale.

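### Section 10.4.1 makes fitness both an input that defines the asthma phenotype clusters and a risk factor for them; if the one scheduled measurement fills both roles, the risk-factor test is circular

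*Protocol*

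**What the plan says.** Three statements in protocol Section 10.4.1 matter.

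- The opening paragraph sets the risk-factor goal: "we will identify risk factors for the asthma phenotypes related to environmental exposures, immune responses and biomarkers, weight and fitness status". Airway and environmental microbiota complete the list.
- Item 2 begins with a narrow set of clustering inputs: "we will perform a cluster analysis to identify patterns of wheezing, allergic sensitization and lung function over time".
- Later in item 2 the set is widened: "symptoms, exacerbations, allergy, immunologic measures, BMI, fitness, psychosocial factors and objective measurements of lung function, spirometry, eNO and IOS will define clusters".

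Section 5.1.9 adds that "The Six-Minute Walk Test will be used at the 14/15-year time point". Section 7.3 places that test at the 14/15-year Visit B, and no other fitness test is scheduled in this phase.

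Section 10.4.1 does not say that a variable used to form the clusters is left out of the risk-factor step, or that a measurement from another age is used there. It names latent class analysis and other clustering techniques as candidates and fixes neither the method nor the number of clusters.

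**The concern.** A clustering algorithm places children in groups so that the groups differ on the inputs. If one of those inputs is then tested against the group label, the test partly rediscovers what the algorithm did. The usual reference distribution assumes that the groups were formed without looking at the tested variable, and here they were not. A statement that low fitness is a risk factor for a given phenotype could then be reported with no true relation behind it.

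Only the risk-factor part of the primary analysis is at stake. The clusters themselves remain a legitimate description of the cohort.

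**Working it through.** **The plan's own figure.** Section 10.5 gives 442 of 609 children retained: 442/609 = 72.6%, which rounds to the stated 73%. No alpha, effect size or power is given for the risk-factor step.

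**The two roles side by side (Section 10.4.1).**

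| Domain | Defines clusters | Risk factor | Overlap |
|---|---|---|---|
| Fitness | yes | yes | by name; one measurement this phase |
| BMI / weight | BMI | weight | by domain |
| Immune | immunologic measures | immune responses, biomarkers | by domain |
| Environmental exposures | no | yes | none |
| Microbiota | no | yes | none |

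**Size, by simulation.**

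- From the protocol: n = 442 (Section 10.5); five phenotypes at age 7 and one more at age 10 (Section 3.2.1), so five or six classes.
- Assumed: ten inputs as single values, not trajectories. Six core inputs (symptoms, exacerbations, allergy, spirometry, eNO, IOS) carry equal-sized classes. Four (immune, BMI, fitness, psychosocial) are independent noise. Separation is the root-mean-square difference between class centres per core variable, in within-class SD.
- Test (assumed): one-way ANOVA of a noise input on the cluster label at 0.05, F = [Σ n_j(x̄_j − x̄)²/(k−1)] / [Σ(x_ij − x̄_j)²/(n−k)]. Degrees of freedom are 4 and 437 for k = 5, and 5 and 436 for k = 6.
- Result: share of tests with p < 0.05. A valid test gives about 5%.

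Several entries in a row come from separately coded runs of 60 to 150 replicates per cell. The Monte Carlo standard error is at most √(0.25/60) = 6.5 points.

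| Setting | False positives (%) at 1 / 1.5 / 2 / 3 SD |
|---|---|
| Latent class, 5 true classes, k = 5 | 84/53/25/7; 74/36/17/5; 74/37/16/8 |
| Latent class, 6 true classes, k = 6 | 84/57/23/11; 85/49/23/10 |
| Latent class, 5 true classes, k = 6 | 91/78/60/52; 86/60/46/35; 85/68/46/44 |
| Latent class, 5 true classes, k by AIC | 61/53/35/18 |
| Latent class, 5 true classes, k by BIC | 6/12/10/5 |
| Gower k-medoids, 5 true classes, k = 5 | 95/90/77/40 |
| Non-input correlated 0.5 with one input, latent class, k = 5 | 41/29/13/8 |
| Same, Gower k-medoids, k = 5 | 69/61/47/18 |

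A k-means check with real classes and correct k gave 97-100% with five other inputs and 50-69% with nine.

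**After separating the roles.** Clustering on the core inputs only gives 3-6%. Refitting without the tested variable gives 0-7% across runs. If BMI and fitness correlate at −0.3 (assumed), removing fitness but keeping BMI still gives 33/14/7/6% (latent class, k = 5); removing both gives 4-6%.

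**Power of a valid test.** For a true 0.5 SD BMI difference in one of five classes, latent class with k = 5 and core inputs only: 33/75/78/93%. Refitting without BMI: 31/70/79/92%.

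**The case against.** The strongest reply is that the circular test is assumed. Section 10.4.1 states its risk-factor goal in one sentence and gives no model, test or alpha; which measurement at which age enters which model is normally settled in the SAP, which is not at hand. It is true that the ANOVA is an assumption made here. But the point is not a missing detail: the protocol itself gives fitness both roles, and an SAP that separated them would have to depart from this text.

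A second reply is that the document contains routes without circularity. The narrow input set in the first sentence of item 2 is one, but the same item then widens it. In Section 1.2, Aim 3a clusters on "upper and lower airway symptoms, allergic sensitization, lung function, BMI and psychosocial factors", and Aim 3b speaks of "linking phenotypes to potential causative factors, such as specific environmental exposures (home microbiome and allergen exposure), AEC DNAm and gene expression patterns". Both lists are open-ended, so they neither contradict Section 10.4.1 nor repair it. Section 10.4.2.2 compares fitness and body habitus by asthma status, which is sound but is a different analysis. The restriction to the first three years of life in Section 10.4.3 covers only the exploratory biomarker model and exempts demographics.

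Three stronger readings are tempting and are not supported.

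- A reader might infer that weight/BMI and immune measures are circular in the same way as fitness. They overlap by domain only. In a birth cohort, early measurements may well be meant as risk factors for later phenotypes.
- A reader might link allergen-specific IgE across the roles, because Section 1.1 counts it among "measures of immune development (PBMC cytokine responses, T regulatory cells, allergen-specific IgE and IgG, plasma cytokines" and Section 10.2.2 has sensitization "defined as a dichotomous variable (aeroallergen-specific IgE by skin test or serum test". Section 1.1 is background on the original design, and Section 10.4.1 names no IgE risk factor.
- A reader might take a false-positive rate above 90% as the expected size. That needs weak separation together with too many clusters or a distance-based method. At 2-3 SD, much of the latent-class inflation at k = 6 comes from forcing six clusters on five classes.

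**Conclusion.** The point holds for fitness: the text gives it two roles, one measurement is scheduled in this phase, and nothing in the protocol separates the roles for Section 10.4.1. If that measurement serves both, the test is circular. For weight/BMI and immune measures the point is conditional on the same or closely correlated measurements, at overlapping ages, being used in both places.

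With the number of latent classes correctly specified, the false-positive rate runs from roughly 75-85% at 1 SD separation to about 5-11% at 3 SD. It rises if k is too large and is near nominal (5-12%) if BIC chooses k. These figures rest on the assumed inputs, class structure and test; their direction does not. The benign case cannot be taken for granted: BIC is named only for the growth trajectories in Section 10.4.2.2, and Section 10.4.3 uses AIC to choose the number of clusters for each variable.

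A reader might infer that the whole primary analysis fails. It does not: phenotype identification, the risk-factor work on environmental exposures and microbiota, and the asthma-status analyses in Section 10.4.2.2 are unaffected. This should be fixed before the clusters are formed.

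**What to change.** In Section 10.4.1, assign each domain, not just each variable, to one role. Two options are open.

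1. Cluster on wheeze or symptoms, sensitization and lung function, as in the first sentence of item 2, and test fitness, weight/BMI and immune measures as risk factors.
2. Keep those domains as inputs and report them descriptively by cluster, with no p-value and no risk-factor claim. Treat close correlates the same way, for example adipokines when BMI is an input. Excluding only the input itself is not enough, as the correlated-measure rows above show.

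Under option 2, a domain kept as an input may be tested in a sensitivity analysis against clusters refitted without that domain and its correlates. Weight and fitness should be removed together. The report must say that the refitted clusters are not the reported phenotypes, so such a result concerns a different outcome.

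The cost is a text change and at most one extra cluster fit per domain, with no new data. Option 1 narrows what the phenotypes describe; option 2 gives up formal tests for the domains kept as inputs. Under either route a valid test has limited power when classes lie close together: about one third at 1 SD in the BMI example above.

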10.4.2 Analysis of Secondary Objectives

10.4.2.1 Early life exposure to household allergens

To determine whether early life exposure to allergens in the home in the absence of a diverse microbiome is associated with sensitization to those allergens and respiratory symptoms (perennial rhinitis and allergic asthma phenotypes), we will examine the association between early-life exposures to allergens and diversity in the microbiome towards allergic sensitization. The assumption is that children with high levels of exposure and low microbiome diversity will have a higher likelihood of early sensitizations. Early sensitizations will be obtained by latent class mixed model analysis combining both skin tests and specific IgEs to aeroallergens. Then a multinomial logit model, with possible adjustments for race and gender, will test the (multiplicative & additive) interaction between these two predictors and the likelihood of early sensitization. Furthermore, these prolonged exposures can have a compound effect in sensitization, and summary measures such as cumulative exposures may not fully capture these relationships. We proposed to extend the model suggested above by using a distributed lag linear (and non-linear) model with flexible exposure-response and lag-response functions to examine the association between sensitization and exposures in early life.

Pathway analysis will be used to determine how a host of environmental factors contribute to the development of rhinitis with specific classifications. Based on medical evidence in the

published literature we will develop and test a conceptual model to describe how different risk factors domains (i.e. allergic inflammation, pulmonary physiology, environmental exposures, etc.) are linked to rhinitis. A causal network analysis will be implemented using structural equations models to simultaneously perform (1) a confirmatory factor analysis in each domain to estimate the relationship between the domain of interest and each observed variable used to measure the domain and (2) a series of regression models to estimate the standardized direct effect of each independent domain onto rhinitis.

10.4.2.2 Effect of pubertal changes in adiposity and sex hormones on lung growth and asthma onset, prevalence and morbidity

Levels of steroid hormones, steroid binding proteins, leptin, adiponectin and serum inflammatory indicators (IL-6, TNF- α , CRP) at 8, 10, 12, 14/15, and 16/17 years of age will be compared to asthma status by ANOVA. These analyses will also be stratified by sex, and we will test whether sex hormones and sex hormone binding proteins modify the relationship between leptin and asthma prevalence in post-pubertal girls and boys. Body habitus and measurements of fitness (6-minute walk in clinic) will also be compared among children with vs. without asthma. We expect that children at greatest risk for asthma will be those with low fitness and activity, high BMI, increased serum inflammatory markers, and atopy.

We will use trajectory analysis to examine whether changes in weight or BMI are related to asthma prevalence in children from age 10 to 17 years. We will use semiparametric mixture modeling—which combines latent growth curve and mixture modeling—to identify growth trajectories over time separately for boys and girls. Trajectory parameters will be estimated using the maximum likelihood approach built upon a binary logit model, using the BIC (Bayesian information criterion) to identify the best model. The objective of model selection is to summarize the distinctive features as parsimoniously as possible. The resulting growth trajectories will be used as predictor variables in a logistic regression model predicting development of asthma. The model will be tested for effect modification by sex.

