2.2 Secondary Objectives

Secondary objectives are:

1. To determine whether early life exposure to allergens in the home in the absence of a diverse microbiome is associated with sensitization to those allergens and respiratory symptoms (perennial rhinitis and allergic asthma phenotypes).
2. To determine the association of pre-pubertal obesity and the effect of pubertal changes in adiposity and sex hormones on lung growth and asthma onset, prevalence and morbidity.

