7.1 Informed Consent

Once the URECA V protocol is approved, informed consent to continue participation will be obtained by the URECA staff at the earliest time that the participant's parent/guardian is seen in person. If the family has not been seen in person and the participant reaches 16 years of age, a telephone consenting procedure will be used to continue with quarterly phone calls, according to IRB requirements. In these cases, written consent will be obtained at the next clinic visit, before any study activity. We will also obtain written assent from participating children according to local IRB guidelines before enrollment into URECA V.

7.2 14/15-Year Clinic Visit A

At the 14/15-year Visit A, questionnaires about the participant's physical health, habits, and environment will be administered. Questionnaires pertaining to stress and mental health will also be administered. A brief physical examination will be conducted, to focus on ears, nose, throat, chest and skin, and including Tanner staging. Urine and blood samples will be collected, supplies and instructions for home dust collection will be distributed, and exhaled nitric oxide will be measured. IOS and spirometry will be performed. Allergen skin testing to a panel of common indoor and outdoor allergens will be performed. Methacholine challenge is planned, with post-bronchodilator spirometry and IOS reversibility being done only when participants do not meet the criteria for methacholine challenge.

7.3 14/15-Year Clinic Visit B

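### Secondary objective 1 asks about sensitization to the allergens the child was exposed to, but no model in Section 10.4.2.1 pairs exposure to an allergen with sensitization to it

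*Protocol*

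**What the plan says.** The question is posed allergen by allergen in three places: Aim 2 in Section 1.2, secondary objective 1 in Section 2.2, and the opening of Section 10.4.2.1. In Section 2.2 the exposure "is associated with sensitization to those allergens and respiratory symptoms (perennial rhinitis and allergic asthma phenotypes").

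The analysis text then broadens the outcome: "we will examine the association between early-life exposures to allergens and diversity in the microbiome towards allergic sensitization". The working hypothesis is that "children with high levels of exposure and low microbiome diversity will have a higher likelihood of early sensitizations". The outcome variable is defined next: "Early sensitizations will be obtained by latent class mixed model analysis combining both skin tests and specific IgEs to aeroallergens". The model follows: "Then a multinomial logit model, with possible adjustments for race and gender, will test the (multiplicative & additive) interaction between these two predictors". The distributed-lag extension is to use "flexible exposure-response and lag-response functions to examine the association between sensitization and exposures in early life", again without naming a specific allergen.

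The sensitization endpoint in Section 10.2.2 is also at child level: any positive test, the number of positive tests, or the sum of sIgE values. Section 10.5 gives the retained sample (442 of 609) but no effect size, prevalence or power for this objective.

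**The concern.** A sensitization class built over aeroallergens measures how atopic a child is and in what pattern. It does not record whether a child exposed to cockroach became sensitized to cockroach. Two consequences follow.

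First, attribution. If the exposure-by-diversity interaction is significant, the result cannot be tied to the allergens in the home, because general atopy would produce it too.

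Second, sensitivity. If exposure acts only on its own allergen, the other tests that shape the classes add variation unrelated to that exposure, and the estimated effect shrinks. A null result would then not refute the objective.

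**Working it through.** **1. The plan's own figure.** 442/609 = 72.6%, which rounds to the stated 73%. I use n = 442 below. Every other input is an assumption.

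**2. Dilution by hand, main effect of exposure.** Assume 20% of unexposed children are positive to each allergen, independent tests, and an allergen-specific OR of 2. Odds rise from 0.25 to 0.50, so the exposed risk is 0.333. As a simple pooled outcome take any positive test among K allergens.

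- K = 3, only one allergen's exposure active: unexposed 1 − 0.8³ = 0.488; exposed 1 − 0.8² × 0.667 = 0.573. Pooled OR = (0.573/0.427)/(0.488/0.512) = 1.41.
- K = 8, same: 1 − 0.8⁸ = 0.832; 1 − 0.8⁷ × 0.667 = 0.860. Pooled OR = 1.24.
- K = 3, all exposures moving together: exposed 1 − 0.667³ = 0.704. Pooled OR = 2.49, so no dilution.

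With actual latent classes (simulation, n = 442, OR 2.5, 2 or 4 classes), the class OR was 1.34–1.52 for K = 3 and 1.12–1.24 for K = 8. The matched OR was about 2.4–2.6.

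**3. The planned interaction.** Section 10.4.2.1 tests exposure by diversity, so I simulated that. Assumptions:

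- Child-level atopy SD 1.5 and intercept −1.5 on the logit scale, so about a quarter of tests are positive.
- Exposure acts only on its own allergen and only in the low-diversity half.
- Two-sided alpha 0.05, 200 cohorts per cell (Monte Carlo standard error at most √(0.25/200) = 3.5 points).
- Pooled analysis: two-class latent class on all tests, then logistic regression on total exposure × diversity.
- Matched analysis: one row per child and home allergen, allergen intercepts, own exposure × diversity, child-clustered standard errors.

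Power in %, pooled v matched, by correlation between exposures:

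| Home allergens | Unaffected outdoor tests | OR per SD | 0 | 0.3 | 0.6 |
|---|---|---|---|---|---|
| 3 | 3 | 1.5 | 7.5 v 70 | 11.5 v 58.5 | 10 v 50 |
| 3 | 3 | 2 | 14.5 v 99 | 18.5 v 97.5 | 21.5 v 91.5 |
| 3 | none | 1.5 | 15 v 70 | 23 v 58.5 | 23.5 v 50 |
| 3 | none | 2 | 31 v 99 | 45.5 v 97.5 | 58.5 v 91.5 |
| 6 | 6 | 1.5 | 9 v 88.5 | 9.5 v 79.5 | 10 v 69.5 |
| 6 | 6 | 2 | 14.5 v 100 | 16 v 100 | 25 v 100 |
| 6 | none | 1.5 | 14 v 88.5 | 21.5 v 79.5 | 30 v 69.5 |
| 6 | none | 2 | 28 v 100 | 49.5 v 100 | 68.5 v 100 |

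The smallest gap in any row is 50 − 23.5 = 26.5 points.

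**4. Stability.** Separate runs of the same design gave 7% v 92% (OR 1.5, independent exposures, outdoor tests included) and 71% v 99% (OR 2, correlation 0.6, home allergens only). In a further set with 6 home and 6 outdoor tests, OR 1.5 and independent exposures gave 5% v 91% with two classes and 5% v 94% with four. OR 2 at correlation 0.6 gave 30% v 98% with two classes and 35% v 97% with four. At correlation 0.9, OR 2 and four classes, power was 36% v 97%. More classes and correlated exposures narrow the gap but do not close it. Matched power is not always high: it stays above 90% at OR 2 but falls to 50% at OR 1.5 with three correlated exposures.

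**The case against.** **Pooling is inferred.** In the sentence that defines the outcome, the two things combined are the test types, skin test and sIgE. Whether the latent class model is fitted per allergen or jointly is not stated. This stands: pooling over allergens is the natural reading but not an explicit one. On either reading, no pairing of exposure and outcome is described.

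**A statistical analysis plan could supply the detail.** It could, but the protocol has already named an outcome and two models, and they do not match the question it asks.

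**A child-level outcome has its own support.** Aim 2 also seeks exposures linked to no sensitization, sensitization without symptoms and sensitization with symptoms, and Section 10.2.2 defines sensitization per child. This is a reason to keep the latent classes, not to let them stand in for the matched question.

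**Stronger readings a reader might infer.**

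- That a single latent class is used. A multinomial logit implies several classes, some of which may partly separate by allergen.
- That outdoor allergens dilute the outcome. Section 7.2 does say "Allergen skin testing to a panel of common indoor and outdoor allergens will be performed", but that is the 14/15-year panel. The protocol does not list the early-life tests that enter the classes.
- That the effect would be diluted close to null. Near-null results need many allergens, largely independent exposures and few classes. For the main effect, with exposures moving together, pooling did not dilute at all.

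**The comparison favours the matched model by construction.** True: the simulated effect is purely allergen-specific, and the classes are cross-sectional rather than from a longitudinal mixed model. The figures show what is lost if the objective's own hypothesis is right, and nothing more.

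**Conclusion.** The mismatch is real. The objective concerns sensitization to the same allergens, and the analysis described does not test that. An association found with the planned outcome could not be attributed to the household allergens, and an allergen-specific effect would generally be attenuated.

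The amount cannot be fixed from the protocol. Over all the interaction settings tried, power was about 5% to 71% for the pooled class and 50% to 100% for matched data. That rests on n = 442 with complete data, OR 1.5 to 2 per SD, 3 to 6 home allergens, exposure correlation 0 to 0.6 (one setting at 0.9), two or four classes, and an effect confined to the matching allergen. No single figure within these ranges should be quoted as the study's power. The attribution problem does not depend on any of these assumptions.

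**What to change.** In Section 10.4.2.1, make the main model for the same-allergen part of the objective allergen-matched:

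- one row per child and home allergen;
- outcome: sensitization to that allergen by skin test or sIgE;
- terms: allergen-specific intercepts, exposure to that allergen, microbiome diversity and their interaction, with the adjustments already foreseen;
- child-clustered standard errors or a child random effect.

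The stacked form gives one interaction test over all allergens. Keep the latent class multinomial model as a supporting analysis of general sensitization. Where the early-life tests include allergens with no home exposure measure, sensitization to those may serve as a negative-control outcome.

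If the matched model is not adopted, reword the objective in Sections 1.2, 2.2 and 10.4.2.1 to general aeroallergen sensitization.

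Cost: analysis wording and modest programming. In this phase skin tests are read per antigen (5.1.2), sIgE is allergen-specific (5.2.1.3) and dust is assayed per allergen (7.8). Section 5.1.1 says the dust assays are unchanged from the original protocol. I assume the early-life data have the same structure. The downside is that the general-atopy question moves to a supporting analysis.
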